8.2 Study Treatment Administration Schedule

Patients will receive 12 mcg/kg of tagraxofusp by IV infusion once daily for 3 consecutive days (or 3 doses over a period not to exceed 10 days if postponement is required to allow for toxicity resolution) of a cycle in the absence of PD or other withdrawal criteria.

A treatment cycle is 21 days in C1-4 and 28 days in C5 and beyond.

The total per-patient dose is calculated based on patient body weight in kg at baseline (C1D1). This dose will be recalculated if there is a 10% or greater change from baseline in body weight.

The first cycle of tagraxofusp must be administered in the inpatient setting, with hospitalization beginning the day of the first infusion of tagraxofusp (or a prior day) and ending approximately 24 hours after the last infusion of tagraxofusp. Subsequent cycles of tagraxofusp can be administered in the inpatient setting or in a suitable outpatient ambulatory care setting that is equipped for intensive monitoring of patients with hematopoietic malignancies undergoing treatment, per the Investigator's discretion, institutional guidelines, and capabilities. Patients will be monitored for at least 1 hour (or longer at the Investigator's discretion) following the administration of each infusion of tagraxofusp in Cycle 2 and beyond.

Patients with evidence of ongoing disease control during treatment (without evidence of clinically significant PD or intolerable toxicity) may receive repeated cycles of tagraxofusp even if an overall response, in the judgment of the Investigator, is not attained.

Refer to [Section 8.2.1](#) for details regarding required pre-medication, patient monitoring procedures, and dose modification procedures for the management of tagraxofusp-related toxicity.

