- 1 The end-of-cycle evaluations (Day 28 or thereafter) may also serve as the pre-infusion evaluations for the subsequent cycles; with the exception of vital signs, these assessments do not need to be duplicated on successive days unless there is an abnormality or other clinically relevant reason for repeat evaluation.
- 2 Disease evaluation via bone marrow aspirate/biopsy and/or imaging studies (when relevant) will occur every 12 weeks (± 7 days). The frequency of bone marrow evaluation may be reduced (obtained less frequently) if peripheral blood, clinical and/or imaging assessments indicate clinical stability, as per the Investigator's discretion in consultation with the Medical Monitor. The frequency of imaging assessments may also be reduced if clinical/laboratory findings indicate stability, as per the Investigator's discretion in consultation with the Medical Monitor.
- 3 Height will be measured at screening only; weight does not need to be measured more than once per day, and should be measured pre-infusion on treatment days. Vital signs should be performed after patient is sitting for 3 to 5 minutes. If during dosing period, vital signs should be taken immediately prior to infusion, at 0 (i.e., immediately after completion of infusion), and at 30 and 60 minutes post-infusion.
- 4 To be collected prior to tagraxofusp infusion if during dosing period. Hematology includes WBC count with differential, RBC count, hematocrit, hemoglobin, platelet count, and immature myeloid cells (including blasts + myelocytes + metamyelocytes + promyelocytes + nucleated red blood cells) (for safety assessments as well as efficacy assessments at the end of each cycle in between bone marrow assessments).
- 5 To be collected prior to tagraxofusp infusion if during dosing period. Serum chemistry includes electrolytes and additional parameters (equivalent to Chem-20): ALT, albumin, alkaline phosphatase, AST, bicarbonate, bilirubin, BUN, calcium, magnesium, chloride, creatinine, glucose, LDH, phosphate, potassium, sodium, total protein, uric acid, chloride, and CPK. See [Appendix Section 18.3](#) for administration of albumin if serum albumin decreases to < 3.0 g/dL (< 30 g/L) during treatment days or in the immediate post-treatment period.
- 6 In lieu of PT, INR may be measured.

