11.12 Tumor Assessments

Tumor assessments must be performed at baseline within 28 days prior to the first administration of tagraxofusp, and on the scheduled specified in [Table 2](#) and [Table 3](#) for Stage 2 and [Table 4](#) and [Table 5](#) for Stage 3A.

Response assessment is performed by means of the following:

- **MF (Stage 2):** The IWG-MRT/ELN 2013 criteria (see [Table 6](#) in Appendix Section 18.1).
- **CMM (Stage 2):** The IWG MDS 2006 criteria (see [Table 7](#) in Appendix Section 18.1).
- **CMM (Stage 3A):** MDS/MPN 2015 criteria (see [Table 8](#) in Appendix Section 18.1).

After Baseline, tumor response assessments are performed at the end of C1 and C4 and then every 12 weeks (± 7 days) thereafter, at End-of-Treatment, and at other timepoints if clinically warranted.

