1.1.2. Study Design

Study STML-401-0314 was initially designed as a 2-stage, non-randomized, open-label, multicenter study of tagraxofusp in patients with subtypes of advanced, high risk MPNs. Initially in this study, patients with CMML and myelofibrosis (MF), as well as systemic

mastocytosis (SM) and advanced symptomatic chronic eosinophilic leukemia, including primary eosinophilic disorders (PED) were eligible for enrollment.

In Stage 1, which is complete at the time of this Statistical Analysis Plan (SAP), only patients with CMML and MF were enrolled. The primary objective of Stage 1 was to establish the maximum tolerated dose (MTD) or the maximum tested dose (MTeD) at which multiple dose-limiting toxicities (DLTs) were not observed. In Stage 2, further characterization of the safety and initial assessment of clinical activity at the recommended phase 2 dose (RP2D) were intended in patients with MF and CMML, with an initial planned sample size of 18 patients in each cohort, then extended to approximately 30 patients in each cohort. Enrollment in Stage 2 is closed.

In Stage 1, 9 patients (5 with CMML and 4 with MF) received tagraxofusp at doses of [REDACTED] via intravenous (IV) infusion on days 1-3 every 21 days for Cycles 1-4, every 28 days for Cycles 5-7, and every 42 days for Cycles 8 and beyond. No MTD was identified in Stage 1 and the MTeD was 12 µg/kg which was considered the RP2D. In Stage 2 of this study, patients received tagraxofusp at the RP2D, 12 µg/kg, on the same schedule as Stage 1. Stage 2 primarily included patients with CMML and MF; 1 SM patient was treated during Stage 2 at the RP2D.

Based on preliminary clinical activity observed and increasing scientific and clinical knowledge of CMML, Stage 3A was added by protocol amendment 7, dated October 21, 2019. Stage 3A enrolled 2 populations of patients with CMML-1 and CMML-2:

1. Previously untreated patients who are high risk and not expected to benefit from hypomethylating agents (HMAs) (previously untreated patients; approximately 20 patients), and
2. Patients who are primary or secondary failures to first-line therapy, including HMAs, hydroxyurea (HU), or intensive chemotherapy (first-line failure patients; approximately 20 patients).

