4.3.2. Duration of Response

Duration of objective response is defined as the time from when the disease specific criteria (see [Section 8](#)) are first met for CR or PR until the date that the criteria for relapse (including SD, progressive disease [PD], or relapse) after CR/PR is met, or death. In the case that SD follows CR/PR and there is no evidence that response rebounds to CR/PR, duration of objective response will end at the time of first reduction of response to below CR/PR. For patients who receive SCT after CR/PR, DOR will include time to disease relapse post-transplant. Patients who are lost to follow-up or who do not relapse after objective response as of the analysis date will be censored on the latter of the date of last treatment with tagraxofusp or date of last disease

assessment recorded prior to the analysis date. If patient starts other anticancer therapies (with the exception of SCT), they will be censored at the latter of the date of last treatment with tagraxofusp or date of last disease assessment recorded that occurred prior to the start of the new therapy.

The distribution of DOR will be estimated by Kaplan-Meier methodology and the 25th percentile, median, and 75th percentile of time to event, number and percentage of events and censored observations, and appropriate 95% CIs will be presented.

For MF patients, the median duration of response for each category of clinical benefit, including clinical improvement, anemia, spleen, or symptom responses, molecular remission, or cytogenetic/molecular relapse, will be derived similar to the duration of objective response. For CMML patients, the median duration of response for each category of clinical benefit, including erythroid, platelet, neutrophil, spleen or symptoms responses, will be derived similar to the duration of objective response.

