4.3.3. Progression-Free Survival

Progression-free survival is defined as the time from the date of first infusion of tagraxofusp to the date of PD or death from any cause, whichever occurred first. For patients who receive SCT, PFS will include time to PD or death post-transplant. Patients who do not progress and are still alive at the time of analysis will be censored on the date of last disease assessment recorded prior to the analysis date. If patient starts other anticancer therapies (with the exception of SCT), they will be censored at the latter of the date of last treatment with tagraxofusp or date of last disease assessment recorded that occurred prior to the start of the new therapy. The distribution for PFS will be estimated by Kaplan-Meier methodology and the 25th percentile, median, 75th percentile, number and percentage of events and censored observations, and appropriate 95% CIs will be presented.

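### DOR, and PFS at new therapy, are censored at the later of last dose and last disease assessment, so a patient can be carried past the last full response assessment

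*SAP*

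**What the plan says.** **DOR (SAP 4.3.2).** A responder who has not relapsed by the analysis date, or who is lost to follow-up, "will be censored on the latter of the date of last treatment with tagraxofusp or date of last disease" assessment before that date. If the patient starts anticancer therapy other than a stem cell transplant, "they will be censored at the latter of the date of last treatment with tagraxofusp or date of last disease assessment recorded" before that therapy. Durations of the component responses (erythroid, platelet, spleen and so on) are to be derived in the same way, so they inherit the rule.

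**PFS (SAP 4.3.3).** Patients alive without progression "will be censored on the date of last disease assessment recorded prior to the analysis date". Patients who start other anticancer therapy are "censored at the latter of the date of last treatment with tagraxofusp or date of last disease assessment recorded" before it.

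**Schedule.** Protocol 11.12: "After Baseline, tumor response assessments are performed at the end of C1 and C4 and then every 12 weeks", plus End-of-Treatment. Protocol 8.2: "A treatment cycle is 21 days in C1-4 and 28 days in C5 and beyond". Note 2 to Protocol Tables 3 and 5 adds, for clinically stable patients: "The frequency of bone marrow evaluation may be reduced (obtained less frequently"). It allows the same for imaging and gives no minimum frequency.

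The SAP does not define a disease assessment for these rules, gives no reason for using the dose date, and plans no sensitivity analysis.

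**The concern.** An infusion is not an observation of response. Protocol 8.2 allows repeated cycles under disease control even where no overall response is attained, so a patient still being dosed is not necessarily still in CR or PR. For CMML, both CR and PR rest on marrow criteria (Protocol Tables 7 and 8). If the last dose falls after the last assessment, the DOR rule counts the days between as time in response. In the new-therapy branch of PFS, those days count as progression-free time.

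Within PFS, a patient who switches therapy can gain days after the last assessment, while a patient who does not switch gains none. SAP 3.5 splits efficacy summaries by treatment-naïve versus relapsed/refractory, and CMML response data also by stage. Single censored times can therefore carry weight in small groups.

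The wording is also loose. Read literally, *latter* means the second-named date, which is the assessment. *Later* is evidently intended, but two programmers could derive different datasets.

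**Working it through.** **Inputs.** Cycle lengths are from Protocol 8.2 and assessment times from Protocol 11.12. Dosing is on Days 1 to 3, extendable to Day 10 (Protocol 5.1, SAP 1.2.1.3). The ±7-day visit window is ignored in steps 1 to 5.

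**1. The plan's own dates.** 4 × 21 = 84 days = 12 weeks. 84 + 3 × 28 = 168 days = 24 weeks. Both match SAP 4.3.7, which pairs C4D21 with 12 weeks and C7D28 with 24 weeks.

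**2. Credited days when no assessment follows the last dose.** Credit = study day of last dose − study day of last scheduled assessment.

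| Last cycle dosed | Last assessment (day) | Day 3 dose: study day, credit | Day 10 dose: study day, credit |
|---|---|---|---|
| C2 | 21 | 24, 3 | 31, 10 |
| C3 | 21 | 45, 24 | 52, 31 |
| C4 | 21 | 66, 45 | 73, 52 |
| C5 | 84 | 87, 3 | 94, 10 |
| C6 | 84 | 115, 31 | 122, 38 |
| C7 | 84 | 143, 59 | 150, 66 |

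C8 to C10 repeat the C5 to C7 pattern from day 168 (C10: 227 − 168 = 59; 234 − 168 = 66). If assessments are thinned under note 2, no upper limit follows from the documents.

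**3. Alternative schedule.** SAP 1.1.2 describes dosing "every 42 days for Cycles 8 and beyond" in Stage 1 and says Stage 2 used the same schedule. SAP 1.2.1.2 gives 28-day cycles from C5 for Stage 2. Those passages need reconciling. With 42-day cycles from C8, the largest credit from C8 on is at C9: 213 − 168 = 45 days, or 220 − 168 = 52.

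**4. If cycle-end counts qualify.** The last assessment is then the end of the previous cycle, and the credit is 3 days (Day 3) to 10 days (Day 10).

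**5. One patient.** Response documented on day 84, last assessed on day 168, last dose on day 227. Time to last assessment: 168 − 84 = 84 days. Time credited: 227 − 84 = 143 days, a ratio of 143/84 = 1.70.

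**6. Direction of the Kaplan-Meier effect.** S(t) is the product of (1 − events/at risk). The events are the same under both rules, and the later-of risk sets are at least as large. The later-of curve is therefore never below the other, and the two coincide if no other patient's event falls in the gap. Illustration with an assumed four responders: events at 56, 84 and 168 days, and one patient censored at day 0 (last assessment) or day 59 (later-of).

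- Last assessment: S(56) = 2/3 = 0.67; S(84) = 2/3 × 1/2 = 0.33.
- Later-of: S(56) = 3/4 = 0.75; S(84) = 3/4 × 1/2 = 0.375.
- The median is 84 days under both.

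**7. Size, by simulation.** Assumptions: exponential DOR with true median 120, 180 or 360 days; assessments every 84 ± 7 days; 10%, 25% or 50% of responders assigned to leave after a dose without a later assessment, unrelated to their response; 20,000 simulated patients per scenario.

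- The mean credit was 34 to 36 days.
- S at day 91 was higher under the later-of rule by 0.3 points (0.850 vs 0.853) to 5.2 points (0.564 vs 0.616).
- The median moved by 0 to 3 days in 8 of 9 scenarios. In the ninth (true median 180 days, 50% leaving) it moved from 175 to 247 days, one assessment interval.

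A check on what this shows: with a true median of 180 days, survival to the first assessment is about 2^(−84/180) = 0.724. The later-of rule gave 0.721 to 0.728 at day 91; the last-assessment rule gave 0.677 to 0.723. With jittered visits and departure unrelated to response, last-assessment censoring itself ran low. The simulation therefore gives the direction and rough size of the difference between the rules, not an error attributable to the SAP's rule.

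**The case against.** The strongest reply is that the rule rarely acts.

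- End-of-Treatment marrow, imaging and response assessment are scheduled. The marrow or imaging waiver applies only if one was done in the previous 4 weeks, so the waiver alone cannot produce a 59-day gap.
- Patients in response at discontinuation continue to be assessed until relapse or progression (Protocol 8.3.2).
- The analysis follows exit of all patients and database lock (SAP 5), so nobody is caught between assessments while on treatment.
- The new-therapy branch is well protected. Other anticancer agents are barred before tagraxofusp stops, apart from limited hydroxyurea use (Protocol 12.3), and the visit at which stopping is decided is itself the End-of-Treatment Evaluation.

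All of this stands. It leaves exposed patients who are lost to follow-up, miss the End-of-Treatment evaluation, or have thinned assessments.

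It is also fair that the gap is not empty. Each cycle end has spleen and liver examination, a symptom score, and blood counts that the protocol labels as efficacy data. Dosing is meant to continue only without progression, so a dose is some evidence for PFS, though not for persisting CR or PR.

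A reader might go further and infer three things that the documents do not support:

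- *That PFS has contradictory rules for one event.* The two branches cover different censoring reasons. The difference lacks a rationale, but it is not a contradiction.
- *That new therapy tends to follow undocumented worsening.* Nothing in either document says so.
- *That reported DOR is inflated by about 70%.* That ratio is one patient's censored time in a chosen worst case, not an effect on any estimate.

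**Conclusion.** The point holds, with limited consequence. Followed as written, and reading *latter* as *later*, the SAP can carry a censored patient as in response (DOR) or progression-free (PFS at new therapy) beyond the last full response assessment. The extent is up to 59 days on the planned 28-day cycles, 66 with dosing to Day 10, and without stated limit if assessments are thinned. It shrinks to about 3 to 10 days if cycle-end counts qualify as a disease assessment, which the SAP leaves open.

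Relative to last-assessment censoring, the Kaplan-Meier curve can only be equal or higher. A material upward bias is not shown. The difference is probably small because most patients should have an assessment after the last dose. How many will not is unknown from the documents; the simulated shares are assumptions. DOR and PFS are secondary (SAP 1.2.5.1), without Type I error control (SAP 3.7), and the analyses are descriptive (SAP 5). The case for change rests on censoring at a date when status was actually evaluated, on one consistent rule, and on an unambiguous derivation.

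**What to change.** In SAP 4.3.2 and 4.3.3, censor DOR and PFS at the date of the last disease assessment before the analysis date or, where it applies, before new anticancer therapy. Delete the reference to the date of last treatment in all three places, which also removes the ambiguous *latter*. Define a disease assessment as one at which the response or progression criteria for that endpoint were evaluated, and state that the same rule governs the component-response durations. The present later-of rule may be kept as a sensitivity analysis, worded as *later*.

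Cost: SAP wording and a change to the censoring derivation. No new data are needed, and ordinary PFS already uses this rule. Some censored times become slightly shorter.

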4.3.3. Progression-Free Survival

Progression-free survival is defined as the time from the date of first infusion of tagraxofusp to the date of PD or death from any cause, whichever occurred first. For patients who receive SCT, PFS will include time to PD or death post-transplant. Patients who do not progress and are still alive at the time of analysis will be censored on the date of last disease assessment recorded prior to the analysis date. If patient starts other anticancer therapies (with the exception of SCT), they will be censored at the latter of the date of last treatment with tagraxofusp or date of last disease assessment recorded that occurred prior to the start of the new therapy. The distribution for PFS will be estimated by Kaplan-Meier methodology and the 25th percentile, median, 75th percentile, number and percentage of events and censored observations, and appropriate 95% CIs will be presented.

